- Holds the appropriate CTEP registration type for the protocol.

Rev. Add8

Additional Requirements

Additional requirements to obtain an approved site registration status include:

- An active Federal Wide Assurance (FWA) number;
- An active roster affiliation with the Lead Protocol Organization (LPO) or a Participating Organization (PO); and
- Compliance with all protocol-specific requirements (PSRs).

Rev. 6/16
Rev. Add8

Downloading Site Registration Documents:

Download the site registration forms from the protocol-specific page located on the CTSU members' website. Permission to view and download this protocol and its supporting documents is restricted based on person and site roster assignment. To participate, the institution and its associated investigators and staff must be associated with the LPO or a Protocol Organization (PO) on the protocol. One way to search for a protocol is listed below.

- Log in to the CTSU members' website (<https://www.ctsu.org>) using your CTEP-IAM username and password;
- Click on the *Protocols* in the upper left of your screen
- Either enter the protocol number in the search field at the top of the protocol tree
- Click on the By Lead Organization folder to expand
- Click on the **ECOG-ACRIN** link to expand, then select trial protocol **EA1131**
- Click on *Documents*, select the *Site Registration* documents link, and download and complete the forms provided.

(Note: For sites under the CIRB, IRB data will load automatically to the CTSU.)

Rev. 6/16
Rev. Add8

Submitting Regulatory Documents

Submit required forms and documents to the CTSU Regulatory Office using the Regulatory Submission Portal on the CTSU website.

To access the Regulatory Submission Portal log in to the CTSU members' website, go to the Regulatory section and select Regulatory Submission.

Institutions with patients waiting that are unable to use the Regulatory Submission Portal should alert the CTSU Regulatory Office immediately at [name] in order to receive further instruction and support.

Required Protocol Specific Regulatory Documents

1. Copy of IRB Informed Consent Document.

NOTE: Any deletion or substantive modification of information concerning risks or alternative procedures contained in the sample informed consent document must be justified in writing by the investigator and approved by the IRB.

2. A. CTSU IRB Certification Form.
Or
B. Signed HHS OMB No. 0990-0263 (replaces Form 310).
Or
C. IRB Approval Letter

NOTE: The above submissions must include the following details:

- Indicate all sites approved for the protocol under an assurance number.
- OHRP assurance number of reviewing IRB
- Full protocol title and number
- Version Date
- Type of review (full board vs. expedited)
- Date of review.

- Signature of IRB official

Rev. Add8

Checking Your Site's Registration Status:

Site registration status may be verified on the CTSU members' website.

- Click on *Regulatory* at the top of the screen;
- Click on *Site Registration*; and
- Enter the sites 5-character CTEP Institution Code and click on Go.
- Additional filters are available to sort by Protocol, Registration Status, Protocol Status, and/or IRB Type.

NOTE: The status shown only reflects institutional compliance with site registration requirements as outlined within the protocol. It does not reflect compliance with protocol requirements for individuals participating on the protocol or the enrolling investigator's status with NCI or their affiliated networks.

Patient Enrollment

Rev. 9/17

Rev. Add7

Treatment should start within 6 weeks (thirty [30] working days) following randomization date.

Rev. Add8

The Oncology Patient Enrollment Network (OPEN) is a web-based registration system available on a 24/7 basis. OPEN is integrated with CTSU regulatory and roster data and with the LPOs registration/randomization systems or the Theradex Interactive Web Response System (IWRS) for retrieval of patient registration/randomization assignment. OPEN will populate the patient enrollment data in NCI's clinical data management system, Medidata Rave.

Requirements for OPEN access:

- A valid CTEP-IAM account;
- To perform enrollments or request slot reservations: Must be on an LPO roster, ETCTN corresponding roster, or participating organization roster with the role of Registrar. Registrars must hold a minimum of an Associate Plus (AP) registration type;
- Have an approved site registration for the protocol prior to patient enrollment.

To assign an Investigator (IVR) or Non-Physician Investigator (NPIVR) as the treating, crediting, consenting, drug shipment (IVR only), or receiving investigator for a patient transfer in OPEN, the IVR or NPIVR must list the IRB number used on the site's IRB approval on their Form FDA 1572 in RCR.

Prior to accessing OPEN, site staff should verify the following:

- Patient has met all eligibility criteria within the protocol stated timeframes; and
- All patients have signed an appropriate consent form and HIPAA authorization form (if applicable).

NOTE: The OPEN system will provide the site with a printable confirmation of registration and treatment information. You may print this confirmation for your records.

Access OPEN at <https://open.ctsu.org> or from the OPEN link on the CTSU members' website. Further instructional information is in the OPEN section of the CTSU website at <https://www.ctsu.org> or <https://open.ctsu.org>. For any additional questions, contact the CTSU Help Desk at [name] or [contact].

- 4.1 Screening (STEP 0)
 - 4.1.1 Protocol Number
 - 4.1.2 Investigator Identification
 - 4.1.2.1 Institution and affiliate name
 - 4.1.2.2 Investigator's name
 - 4.1.3 Patient Identification
 - 4.1.3.1 Patient's initials (first and last)
 - 4.1.3.2 Patient's Hospital ID and/or Social Security number
 - 4.1.3.3 Patient demographics
 - 4.1.3.3.1 Gender
 - 4.1.3.3.2 Birth date (mm/yyyy)
 - 4.1.3.3.3 Race
 - 4.1.3.3.4 Ethnicity
 - 4.1.3.3.5 Nine-digit ZIP code
 - 4.1.3.3.6 Method of payment
 - 4.1.3.3.7 Country of residence
 - 4.1.4 Eligibility Verification

Patients must meet all of the eligibility requirements listed in Section [3.1](#).
- 4.2 Additional Requirements
 - 4.2.1 Patients must provide a signed and dated, written informed consent form.

NOTE: Copies of the consent are not collected by the ECOG-ACRIN Operations Office – Boston.
 - 4.2.2 Pathological materials are required to be submitted no later than 21 weeks post-surgery for PAM50 analysis as indicated in Section [10.2](#).

NOTE: The EA CBPF will notify the ECOG-ACRIN Operations Office and submitting institution of receipt of the tumor tissue specimen. PAM50 results will not be reported to the submitting institution.

Patients cannot proceed with randomization to STEP 1 until the EA CBPF confirms receipt of tumor tissue for PAM50 analysis.

Pathological materials will also be used for retrospective central review for confirmation of ER, PR, and HER2 status.
- 4.3 Randomization (STEP 1)
 - 4.3.1 Protocol Number
 - 4.3.2 Investigator Identification
 - 4.3.2.1 Institution and affiliate name.

Rev. 2/16, 6/16
Rev. 9/17
Rev. Add7

Rev. Add8

4.3.2.2 Investigator's name.

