| 
The most current version of the study protocol and all supporting documents must be downloaded from the protocol-specific Web page of the CTSU Member Web site located at https://www.ctsu.org. Access to the CTSU members' website is managed through the Cancer Therapy and Evaluation Program - Identity and Access Management (CTEP-IAM) registration system and requires user log on with CTEP-IAM username and password.
 | | |
| 
For clinical questions (i.e. patient eligibility or treatment-related) contact the Study PI of the Coordinating Group.
 | | |
| 
For non-clinical questions (i.e. unrelated to patient eligibility, treatment, or clinical data submission) contact the CTSU Help Desk by phone or e-mail: CTSU General Information Line – [name], or [contact]. All calls and correspondence will be triaged to the appropriate CTSU representative.
 | | |
| 
The CTSU Web site is located at https://www.ctsu.org
 | | |

Rev. 6/16

Rev. 6/16
Rev. Add#5
Rev. Add6
Rev. Add7

Schema

Accrual = 775
1 cycle = 3 weeks

1. TNBC: ER/PR 1 to $\leq 10\%$ positive staining with weak intensity score, or $\leq 1\%$ positive staining; HER2 negative per ASCO guidelines.
 2. Taxane \pm anthracycline based; platinum agents or capecitabine not allowed.
 3. Tumor tissue from the residual disease on the definitive surgical specimen must have been received by ECOG-ACRIN Central Biorepository and Pathology Facility (EA CBPF) for PAM50 analysis/ determination of patient eligibility as outlined in Section 10. Patients cannot be randomized to treatment until institution receives confirmation of tissue receipt/ eligibility from ECOG-ACRIN.tion 10.2.
 4. Females of child-bearing potential must have a blood test or urine study within 2 weeks prior to treatment initiation to rule out pregnancy.
 5. Radiation therapy (when applicable) may be completed before or after protocol treatment. If performed before protocol treatment, it needs to be completed prior to randomization.
 6. Choice of platinum agent will be per treating physician discretion.
 7. Primary endpoint: IDFS in patient with basal-like TNBC.
 8. Secondary endpoints: IDFS in patient with non-basal-like TNBC, OS and RFS.
- **Arm A closed to new accrual in Addendum #3. New patients are randomized to Arm B or C

1. Introduction

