- After assignment of randomization patients must begin Cycle 1/ Day 1 (platinum based or capecitabine chemotherapy) within 6 weeks (30 working days) of the **randomization date**.
- Randomization occurs no more than 24 weeks from main surgery date (i.e. subsequent surgeries for re-excision of margins or lymph nodes or reconstruction do not apply)

Rev. Add8

Rev. 2/16, 6/16
Rev. 9/17
Rev. Add8
Rev. Add#5

_____ 3.2.1 Must have confirmation from EA CBPF of receipt of formalin-fixed paraffin-embedded tumor tissue specimen (FFPE) of the residual disease in the breast resected at the time of definitive surgery.

_____ 3.2.2 ECOG Performance Status 0 or 1 within 2 weeks prior to randomization.

Rev. 9/17

_____ 3.2.3 Radiotherapy, if applicable, may be given before or after protocol treatment. When radiotherapy is planned prior to protocol treatment administration, patients must have completed adjuvant radiotherapy \geq 2 weeks prior to randomization for protocol therapy, if applicable.

_____ 3.2.4 Patients must have completed treatment with any investigational agent \geq 30 days prior to randomization for protocol therapy initiation (Cycle 1/ day 1).

Rev. 2/16
Rev. Add8

_____ 3.2.5 Patients must be randomized within 24 weeks from main surgery date (i.e. subsequent surgeries for re-excision of margins or lymph nodes or reconstruction do not apply).

- Rev. 6/16 _____ 3.2.6 Women must not be pregnant or breast-feeding due to risk of teratogenicity/ toxicity with capecitabine or platinum-based therapy. All females of childbearing potential must have a blood test or urine study within 2 weeks prior to randomization to rule out pregnancy.
- 3.2.6.1 A female of childbearing potential is defined as any woman that has achieved menarche at some point, regardless of sexual orientation or whether they have undergone tubal ligation, who meets the following criteria: 1) has not undergone a hysterectomy or bilateral oophorectomy; or 2) has not been naturally postmenopausal for at least 24 consecutive months (i.e., has had menses at any time in the preceding 24 consecutive months).
Female of child bearing potential? _____(Yes or No)
- 3.2.6.2 Date of pregnancy blood test or urine study (if not applicable, write N/A instead of date): _____

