4.5 Instructions for Patients who Do Not Start Assigned Protocol Treatment

If after randomization a patient does not receive any assigned protocol treatment, baseline and follow-up data will still be collected and must be submitted through Medidata Rave and EASEE-PRO according to the schedule in the EA1131 Forms Completion Guidelines.

5. Treatment Plan

Rev. 6/16

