7.1 Therapeutic Parameters

NOTE: A window of +/- 3 working days is allowed for all below procedures **unless otherwise specified in the calendar itself**, to account for holidays, vacation, and scheduling issues.

Rev. 9/17
Rev. 6/16
Rev. Add#5
Rev. Add6
Rev. Add7
Rev. Add8

| | STEP 0-Screening | | STEP 1-Randomization | | | | | | | All Patients |
|--|-----------------------------------|---------------------------------------|--|---------------|---------------|---------------|---|---|--|-----------------|
| | All Patients | | For Arms B and C | | | | | | | |
| | Within 8 weeks prior to Screening | Within 2 weeks prior to Randomization | Day 1 of Each Treatment Cycle ¹ | Day 1 Cycle 1 | Day 1 Cycle 3 | Day 1 Cycle 6 | End of Treatment (28 ±7 working days) post treatment discontinuation) ¹³ | 6 months (±4 weeks) after chemotherapy initiation | 15 months (±6 weeks) after chemotherapy initiation | |
| CLINICAL EVALUATIONS | | | | | | | | | | |
| Demographics | X | | | | | | | | | |
| History and Physical | X ¹ | X ¹ | X | | | | X | | | X |
| Vital Signs and Weight | | X ¹ | X | | | | X | | | |
| Height | | X | | | | | | | | |
| ECOG Performance Status | X ¹ | X ¹ | X | | | | X | | | |
| Toxicity Assessments | | | X | | | | X | | | |
| Concomitant Medications Assessments | | | X | | | | X | | | |
| Non-Protocol Anti-Cancer Medications Assessments | | | X | | | | | | | X ¹¹ |
| FBSI PRO | | | | X | X | | | X | X | |
| Medication Adherence Scale PRO ¹⁵ | | | | | X | X | | | | |
| NTx PRO ¹⁴ | | | | X | X | | | X | X | |
| Ov Function PRO ¹⁶ | | | | X | | | | | X | |

| | STEP 0-Screening | | STEP 1-Randomization | | | | | | | |
|--|---|---------------------------------------|--|---------------|---------------|---------------|---|---|--|--|
| | All Patients | | For Arms B and C | | | | | | All Patients | |
| | Within 8 weeks prior to Screening | Within 2 weeks prior to Randomization | Day 1 of Each Treatment Cycle ¹ | Day 1 Cycle 1 | Day 1 Cycle 3 | Day 1 Cycle 6 | End of Treatment (28 ±7 working days) post treatment discontinuation) ¹³ | 6 months (±4 weeks) after chemotherapy initiation | 15 months (±6 weeks) after chemotherapy initiation | Arm A: post randomization to 10 years Arm B and C: 6 months to 10 years from chemotherapy initiation ⁷ |
| Tobacco Use Assessment PROs ¹⁷ | See Section 5.6 | | | | | | | | | |
| LABORATORY/ RADIOLOGICAL ASSESSMENTS | | | | | | | | | | |
| Serum or Urine Pregnancy Test ⁴ | | X | | | | | | | | |

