- Rev. 6/16 1. Each cycle is a 3-week period of time. Total number of treatment cycles is 6 for the capecitabine arm and 4 for the platinum agents. Chemotherapy must be initiated within 6 weeks (30 working days) following randomization. CBC, chemistries and INR (**INR is only necessary for patients on warfarin that are on Arm C**) should be done ≤ 8 weeks prior to screening, ≤ 2 weeks prior to randomization, and during treatment, it should be done within 3 days prior to each treatment cycle. Telehealth visits are acceptable as long as ECOG status, vital signs, height and weight are current (i.e. performed within 8 weeks) on Day 1 of each cycle. Additionally, treatment initiation may be delayed for up to 10 days without requiring repeat labs/ clinic visit/ clinic assessments in the following special circumstances: inclement weather, holidays, COVID-related issues, delay in drug delivery from specialty pharmacies for patients on Arm C (capecitabine), and insurance approval delays.
- Rev. Add8
- Rev. 6/16 2. Pre-study CBC (with differential and platelet count) includes WBC, ANC, Platelets, Hgb, and Hct or PCV
- Rev. 6/16 3. All required chemistries include sodium, potassium, chloride, bicarbonate (also known as CO₂ or carbon dioxide), BUN, creatinine, glucose, total bilirubin, calcium, magnesium, total protein, albumin, AST, ALT, and alkaline phosphatase.
- Rev. Add8 4. For patients of childbearing potential; must be done within 2 weeks prior to randomization.
- Rev. 6/16 5. Cisplatin or Carboplatin (Arm B only); per treating physician’s discretion. Growth factor use is allowed per ASCO guidelines.
- Rev. Add8 6. Tumor tissue collection is mandatory and required to be submitted to the ECOG-ACRIN Central Biorepository and Pathology Facility (EA CBPF) as outlined in Section [10.2](#). Confirmation of receipt of tumor tissue will be forwarded to the ECOG-ACRIN Operations Office and submitting institution. The CLIA Laboratory Sample Submission Form ([Appendix IV](#)) must be submitted with the tumor tissue. Results of PAM50 analysis will not be reported to the submitting institution. Two Streck tubes of peripheral blood must be collected on all patients at the following two time points: on or before cycle 1 day 1 of protocol chemotherapy and around 6 months after protocol chemotherapy initiation.

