- Rev. Add8 7. Every 3 months (± 2 weeks) if patient is < 2 years from study randomization, every 6 months (± 4 weeks) if patient is 2-5 years from study randomization, every 12 months (± 6 weeks) if patient is 5-10 years from study randomization. No other specific requirements are needed if patient is more than 10 years from study randomization. If a recurrence (locoregional or distant) occurs prior to 10 years from randomization, patient will be followed for survival (until year 10) but no other protocol procedures (clinic visits, blood collections, etc.) will be necessary.
8. All specimens submitted must be entered and tracked via the online ECOG-ACRIN Sample Tracking System (STS) as outlined in Section [10.3](#).

9. In case of a local recurrence or clinical suspicion of distant recurrence, imaging tests to exclude presence of distant recurrent disease are strongly recommended, but should be performed at the investigator's discretion.
- Rev. 6/16 10. If Baseline CBC, INR (**INR is only necessary for patients on warfarin that are on Arm C**) and CMP were performed within 3 days of Day 1 Cycle 1 of treatment initiation, there's no need to repeat them on Day 1 Cycle 1
11. Determination if any anti-cancer treatment is being administered beyond 3 months from randomization, which was not specified in the protocol.
12. Only for patients on warfarin therapy and Arm C
- Rev. Add8 13. End of treatment visit should be scheduled 28 (+/- 7 working days) from Day 1 of last administration of platinum agent in Arm B, and 28 (+/- 7 days) from the last administered treatment dose for Arm C; regardless if patients completed treatment or if treatment was interrupted due to toxicities or other causes.
14. For Arm B (platinum chemotherapy) only
15. For Arm C (capecitabine) only
16. Women age < 55 years old only would answer 8 questions on Day 1 Cycle 1, and 5 questions 15 months after the initiation of chemotherapy.
17. Tobacco use assessment PROs will be collected using EASEE-PRO; no other EA1131 study PRO will be collected using EASEE-PRO.
18. Kits will be provided for the collection and shipment of peripheral blood specimens. See Section [10](#) for instructions.
19. Submit from patients who answer 'Yes' to 'I agree to provide additional samples for research' in the informed consent.

8. Drug Formulation and Procurement

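### The calendar times the pregnancy test to randomization only, so a site can give the first dose on a test up to 56 days old, against the Schema's 14-day limit

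*Combined protocol and SAP*

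**What the plan says.** Four places in the combined protocol and SAP bear on the timing of this test.

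- **Schema, note 4:** "Females of child-bearing potential must have a blood test or urine study within 2 weeks prior to treatment initiation to rule out pregnancy". The limit runs back from the first dose.
- **Section 3.2.6 (eligibility for randomization, Step 1):** "All females of childbearing potential must have a blood test or urine study within 2 weeks prior to randomization to rule out pregnancy". The limit runs back from randomization. The reason given is the risk of teratogenicity and toxicity with capecitabine or platinum.
- **Section 7.1 calendar:** the row "Serum or Urine Pregnancy Test" has one mark, in the column for the 2 weeks before randomization. There is none under Day 1 Cycle 1 or Day 1 of each cycle. Footnote 4, the only footnote on that row, reads "For patients of childbearing potential; must be done within 2 weeks prior to randomization".
- **Section 3.2, opening bullets:** after assignment, patients "must begin Cycle 1/ Day 1 (platinum based or capecitabine chemotherapy) within 6 weeks (30 working days) of the" randomization date. Footnote 1 of the calendar repeats the 6-week limit.

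Other safety tests are re-timed to dosing. Footnote 1 asks for the blood count and chemistries within 3 days before each cycle. Footnote 10 waives the Cycle 1 repeat only if the baseline blood count, INR (where applicable) and "CMP were performed within 3 days of Day 1 Cycle 1 of treatment initiation".

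**The concern.** The stated purpose of the test is to avoid exposing a pregnancy to cytotoxic drugs, so the date that matters is the first dose. Only the Schema note uses that date. The signed eligibility checklist has space for one pregnancy-test date (3.2.6.2), and the calendar schedules one test, before randomization. A site can complete both correctly and still miss the Schema requirement, because nothing in either prompts a second test when the start of treatment slips.

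The population makes this relevant. Section 1.8 expects 60% or more of patients to be premenopausal at diagnosis, and 3.2.6.1 defines childbearing potential broadly. What is at stake is fetal exposure to a teratogenic regimen that a test close to dosing would have prevented.

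**Working it through.** The plan states no figure for the age of the test at first dose, so there is none to reproduce. The check is interval arithmetic.

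**Inputs**

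- Eligibility test: *a* days before randomization, 0 ≤ *a* ≤ 14 (3.2.6; 7.1 footnote 4).
- First dose: *g* days after randomization, 0 ≤ *g* ≤ 42 (3.2 and 7.1 footnote 1: 6 weeks × 7 = 42 days; the bracketed 30 working days agrees at 5 per week).
- Schema limit on the age of the test at first dose: 14 days (note 4).
- Repeat tests scheduled between randomization and first dose: none.

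**Formula**

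Age of the test at first dose = *a* + *g*. The eligibility test alone satisfies note 4 only when *a* + *g* ≤ 14.

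**Results**

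| Case | *a* | *g* | Age at first dose | Over the 14-day limit |
|---|---|---|---|---|
| Schema note 4 followed (repeat if needed) | – | – | at most 14 days | 0 |
| Test on the day of randomization, start at 6 weeks | 0 | 42 | 42 days | 42 − 14 = 28 days |
| Both windows used in full, no repeat | 14 | 42 | 14 + 42 = 56 days | 56 − 14 = 42 days |

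From the inequality, any first dose more than 14 days after randomization exceeds the Schema limit unless the test is repeated, even if the eligibility test was done on the day of randomization. If that test was done 14 days before randomization, only a same-day start meets the limit.

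Section 7.1's general window of plus or minus 3 working days is not added, because it gives way where the calendar states its own timing, as footnote 4 does.

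**The case against.** **No contradiction.** Both rules can be met together, and a site that meets both has a test at most 14 days old at first dose. That stands. A reader might infer that the rules are incompatible, or that 3.2.6 is wrong; the documents support neither. A test after randomization cannot be a criterion for randomization, so 3.2.6 is sound as an eligibility check. What remains is that the calendar, which schedules procedures through treatment, omits a requirement stated elsewhere as mandatory.

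**The Schema may be the out-of-date text.** The margin mark nearest footnote 4 is Addendum 8, while those at the Schema stop at Addendum 7, so randomization may be the later intended anchor. Margin marks can shift in extraction, so this is only suggestive. If it is right, the text still needs correcting, and that reading would accept up to 56 days between test and first dose.

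**Other safeguards exist.** Contraception is advised (3.2.7), a history and physical is scheduled on Day 1 of each cycle, and protocol therapy stops if the patient becomes pregnant (5.7). These reduce the risk but do not replace a test; stopping works only once the pregnancy is known.

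**The 10-day allowance.** Footnote 1 says "treatment initiation may be delayed for up to 10 days without requiring repeat labs/ clinic visit/ clinic assessments in the following special circumstances". A reader might infer that this stretches a compliant test to 14 + 10 = 24 days, or the worst case to 56 + 10 = 66 days. The documents do not support either figure. Footnote 1 is attached to the blood count, chemistries and INR rows and names those tests, while the pregnancy row carries only footnote 4. Nothing says the 10 days extend the 6-week limit.

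**Conclusion.** The point holds as a gap between the Schema and the calendar. A site following the checklist and calendar can give the first dose on a pregnancy test up to 56 days old, against 14 days under Schema note 4, an excess of up to 42 days. The 56 days is a maximum that assumes both windows are used in full and no unscheduled repeat is done. The documents give no distribution of the interval from randomization to first dose, so neither the frequency of late tests nor the number of exposed pregnancies can be estimated.

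The change should be made: following the calendar as written can breach a stated safety requirement, and the remedy is cheap. A reader might infer some bearing on the trial's inference; there is none, because the timing of this test does not enter the definition of invasive disease-free survival, the sample size or the monitoring boundaries.

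**What to change.** Two edits in Section 7.1:

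1. Add a Cycle 1 Day 1 mark to the pregnancy-test row.
2. Amend footnote 4 so that, besides the eligibility test, patients of childbearing potential need a negative test within 2 weeks before the first dose, repeated if the eligibility test is older than that.

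Leave 3.2.6 and Schema note 4 unchanged. No new instruction for a positive result is needed: 5.7 already bars protocol therapy in pregnancy, and Section 4.5 covers follow-up: "If after randomization a patient does not receive any assigned protocol treatment, baseline and follow-up data will still be collected".

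The cost is one extra urine or blood test for patients of childbearing potential who start more than 2 weeks after the eligibility test. It can usually be done with the blood count and chemistries already due within 3 days before Cycle 1, so it should seldom need a separate visit.

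Rewording the Schema to match 3.2.6 would also make the text consistent, but it would leave the 56-day maximum in place and is not preferred.
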